Based on the literature and our own experience we estimated an approximate occlusion rate of 20% with the standard treatment (saline + heparinized saline flush as described above). The power analysis conducted by [name] determined that, using a two-group normal approximation test of proportions with a one-sided .05 significance level, a sample size of 198 participants per group will have 80% power to reject the null hypothesis that the proposed method is not inferior (i.e. the difference in proportions between the proposed method and the standard method is greater than 0.10). Thus, we will continue data collection until 198 have been completed in each group for a total of 396 study participants who completed 6 months of data collection. To date (July 3, 2019), 69.7% of patients enrolled in the study are able to complete 6 months of data collection without withdrawing for an exclusion criterion (ex: transferring to hospice, being started on an anticoagulant, etc). Therefore, we plan to consent 575 patients to result in 396 who complete the study. Once 396 patients have completed 6 months of data collection will stop and any remaining active participants will be withdrawn from the study.

Data Collection:

Independent Variables: Method for flushing implanted port catheters:

• 20 mL of saline followed by 5 mL of Heparinized saline in a concentration of 100 units/mL

OR

• 20 mL of saline only

Dependent Variables:

Primary Outcomes

- Occurrence of first complete (can neither withdraw blood nor flush the catheter) occlusion
- Occurrence of first partial (able to flush but unable to withdraw blood) occlusion
- Frequency with which alteplase (CathFlo) has to be utilized to resolve an occlusion

Secondary Outcomes

- Number of subsequent occurrences of complete or partial occlusions after the first occurrence.
- Amount of time in days that a port remains patent (flushes easily and able to obtain a blood return).
 - Amount of time between entrance in study and first incidence of partial or complete occlusion
 - Amount of time between incidences of partial or complete occlusion.
- Occurrence of other complications:
 - Central Line-Associated Blood Stream Infection (CLABSI) a laboratory-confirmed (recognized pathogen cultured from one or more blood cultures; organism cultured from blood is not related to an infection at another site) blood stream infection that is considered central line associated (CDC, 2012).
 - Develops complication related to Heparin

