With each visit to the identified treatment center, the nurse will document the date and characteristics related to the patency of the port catheter on the Record of Flushes data collection tool. In the event the blood withdrawal is sluggish or absent, the patient will receive a dose of alteplase (CathFlo) according to the data collection site's policy as ordered by the physician. Dosage and results of that intervention will also be recorded on the Record of Flushes data collection tool. In the event that any study participant (regardless of group assignment) requires alteplase (CathFlo) on three (3) consecutive visits to the treatment center, the patient's participation in the study will be terminated and they will be excluded from further data collection. The patient will be returned to a standard maintenance protocol for flushing of the port as prescribed by the afore-mentioned site policy or as prescribed by attending physician.

Participants in the control group will have yellow colored data collection Face Sheets while participants in the intervention group will have blue colored data collection Face Sheets. The Record of Flushes sheet will be white for patients in both groups. A blue or yellow sticker will be placed on the cover of the patient folder housed in treatment center noting the patient's involvement in the study. The data collection Face Sheet and the current Record of Flushes sheet will be kept in the individual patient folder as long as they remain a participant in the study. As the Record of Flushes data sheet becomes full, they will be collected by study staff and placed in locked drawer in a TriHealth or UCMC Barrett Infusion center office.

In January 2018, UCMC Barrett Infusion Center was added as a new site. The study nurses at UCMC Barrett Infusion Center will use the same data collection forms and will store them along with completed informed consent forms at a locked office at UCMC Barrett Infusion Center. Periodically, the lead research coordinator will bring de-identified data collection forms back to TriHealth. Signed informed consent forms will remain locked on UCMC Barrett Infusion Center property.

Experimental Aspect of the Study:

Patients who agree to participate in this study will be randomized to either the control group or intervention group as explained above.

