Potential risks for study participants in either arm of the study include partial occlusion (can instill flush solution but not withdraw blood) and complete occlusion (can neither instill flush solution nor withdraw blood). Study participants could require removal of the port if an occlusion cannot be resolved, and possibly require re-insertion of a new implanted port. In the event of any occlusion, alteplase (CathFlo) in the policy established dose and frequency (see Appendix A) will be instilled to resolve the occlusion. Study participants whose implanted ports are found occluded on three (3) consecutive visits to the treatment center will be excluded from further data collection, i.e., their participation in the study will be terminated. The standard flushing as prescribed by the site's policy or as prescribed by the attending physician will be used. Study participants whose occlusion cannot be resolved with alteplase and require removal of the port will also be terminated and excluded from further data collection. Patients who develop port infections necessitating port removal will be terminated and excluded from further data collection. Study participants who develop HIT (heparin induced thrombocytopenia) or other heparin allergy will be terminated and excluded from further data collection. Likewise, patients who have thrombotic or embolic phenomenon requiring therapeutic anticoagulation will be terminated and excluded from further data collection. If a participant in the intervention group receives clinical care and their port is flushed with heparin (following standard hospital policy), the participant will be withdrawn from the study.

The study will be closed if there is evidence that study participants in the intervention arm experience implanted port occlusion at a disproportionate rate. The amount of alteplase (CathFlo) used in each group will be assessed each

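### Ending data collection after three consecutive alteplase or occluded visits truncates the recurrent counts according to outcome, and the analysis plan makes no provision for it

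*Combined protocol and SAP*

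**What the plan says.** All references are to the combined protocol and SAP.

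- **Data collection tool.** In either group, anyone who "requires alteplase (CathFlo) on three (3) consecutive visits to the treatment center, the patient's participation in the study will be terminated"; "they will be excluded from further data collection". Then "The patient will be returned to a standard maintenance protocol for flushing of the port", under site policy or as the attending physician prescribes. Alteplase is given for slow as well as absent blood return.
- **Experimental Aspect of the Study.** The rule appears again with a different trigger: "Study participants whose implanted ports are found occluded on three (3) consecutive visits to the treatment center will be excluded from further data collection". Ports removed for unresolved occlusion also leave data collection.
- **Dependent Variables.** One primary outcome is "Frequency with which alteplase (CathFlo) has to be utilized to resolve an occlusion". One secondary outcome is "Number of subsequent occurrences of complete or partial occlusions after the first occurrence".
- **Monitoring (Experimental Aspect of the Study).** "The amount of alteplase (CathFlo) used in each group will be assessed each" month. No denominator, threshold or data source is given. The formal interim looks use first partial plus first complete occlusion.
- **Statistical Analysis.** Groups are compared by t-test, chi-square or Fisher's exact test. No method for unequal follow-up or recurrent events is named, and nothing is said about participants terminated early.

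**The concern.** A port that occludes at visit after visit stops contributing at its third consecutive dose, while a port that occludes on and off keeps accruing and can finish with a higher count. Follow-up length thus depends on the outcome, and a comparison of mean counts treats a shortened record as a complete one. Meeting the rule is a clear sign of failed maintenance, yet it is not itself an outcome.

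If saline ports occlude more often and at least as persistently, the recorded excess in doses and repeat occlusions is too small. That is the situation in which a trial of saline most needs these outcomes to be right. A monthly tally drawn from the same forms would lose the same doses.

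**Working it through.** **1. The plan's own figure.** With 20% in both arms, margin 0.10, one-sided 0.05 and 80% power:

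n = (1.645 + 0.842)² × 2 × 0.20 × 0.80 / 0.10² = 6.183 × 0.32 / 0.01 = 197.8, so 198 per group, as stated.

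This concerns a proportion of participants with occlusion. A first occlusion comes before any run of three, so the rule cannot alter it.

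**2. Model for the counts.** The documents give neither visit frequency nor recurrence, so these are assumptions:
- 5% of control and 10% of saline ports are persistent occluders, needing alteplase at each visit with probability p = 0.5, 0.7 or 0.9.
- All other ports have p = 0.02.
- There are V = 8 or 12 visits in 6 months.

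The mean full count per port is V × p. The mean recorded count is p × (expected visits before the stop). Expected visits are s₀ + s₁ + … + s(V−1), where s(v) is the chance of no run of three by visit v:

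s₀ = s₁ = s₂ = 1; s(v) = (1 − p)[s(v−1) + p·s(v−2) + p²·s(v−3)].

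**3. Worked case, V = 8, p = 0.7.**
- Expected visits = 3 + 0.657 + 0.554 + 0.451 + 0.348 + 0.281 = 5.291.
- Persistent port: full 8 × 0.7 = 5.600; recorded 0.7 × 5.291 = 3.704. Other ports: 8 × 0.02 = 0.160 either way.
- Full means: control 0.05 × 5.600 + 0.95 × 0.160 = 0.432; saline 0.10 × 5.600 + 0.90 × 0.160 = 0.704. Difference 0.272, ratio 1.63.
- Recorded means: 0.337 and 0.514. Difference 0.177. Lost: 1 − 0.177/0.272 = 35%.
- Recorded per-visit rates: control 0.337/7.865 = 0.0429; saline 0.514/7.729 = 0.0666. Ratio 1.55.
- Expected t statistic at 198 per arm, difference / √[(sum of the two variances)/198]: full 0.272/√[(1.639 + 2.973)/198] = 1.78; recorded 0.177/√[(0.786 + 1.353)/198] = 1.70.

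A simulation of 300,000 ports per arm agrees: 0.274 recorded as 0.180.

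**4. Range, same formulas.**

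| V | p | Full difference | Recorded | Lost | Rate ratio, full to recorded | t statistic, full to recorded |
|---|---|---|---|---|---|---|
| 8 | 0.5 | 0.192 | 0.161 | 16% | 1.55 to 1.51 | 1.67 to 1.66 |
| 8 | 0.7 | 0.272 | 0.177 | 35% | 1.63 to 1.55 | 1.78 to 1.70 |
| 8 | 0.9 | 0.352 | 0.158 | 55% | 1.69 to 1.54 | 1.84 to 1.69 |
| 12 | 0.5 | 0.288 | 0.208 | 28% | 1.55 to 1.48 | 1.74 to 1.67 |
| 12 | 0.7 | 0.408 | 0.196 | 52% | 1.63 to 1.49 | 1.82 to 1.64 |
| 12 | 0.9 | 0.528 | 0.155 | 71% | 1.69 to 1.44 | 1.86 to 1.60 |

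At 12 visits, raising p from 0.5 to 0.9 increases the full difference but lowers the recorded one.

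**5. A second model, to test direction.** Here the chance of occlusion depends on whether the port was occluded at the previous visit (simulated; 12 visits; first-occlusion risk 20% control, 30% saline). Difference in mean doses, saline minus control:
- Recurrence 0.5 in both arms: 0.221 recorded as 0.195; ratio of means 1.56 to 1.55.
- Recurrence 0.3 control, 0.6 saline: 0.428 recorded as 0.310; ratio 2.43 to 2.06.
- Recurrence 0.7 control, 0.4 saline: −0.038 recorded as +0.074.
- Equal risk (20%) and recurrence (0.5) in both arms: no difference is created.

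The first-occlusion difference is the same with and without the rule when everyone is analysed. If only 6-month completers are analysed, a difference of 0.098 appears as 0.034 (recurrence 0.3 versus 0.6).

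**The case against.** The rule applies to both arms alike, and nothing in the documents says that saline ports are the more persistent occluders. A reader might infer that the rule always understates a difference, or always favours saline. It does not: the third case in step 5 goes against saline, and equal arms stay equal. This part of the objection stands.

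A reader might also infer that the non-inferiority conclusion is compromised. The documents do not support that. The only margin is on the occlusion rate, alteplase counts have no margin, and the formal interim looks use first occlusions. The caveat is that completion is defined as 6 months of participation and the target of 396 is counted in completers, while no analysis set is stated. The protection therefore depends on keeping terminated participants in.

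Truncation also removes variance, so detectability falls much less than the lost share of the mean difference suggests. That stands, but an estimate of a primary outcome should still be right.

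On monitoring, a terminated port has already contributed at least three doses, and the review's data source is not stated. Loss from that tally is therefore possible, not shown.

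Finally, continued follow-up does not recover the full differences in step 4, which assume that the assigned flush continues for 6 months. After the stop, saline participants return to site policy or to what their physician prescribes. Nor should one assume that the flush is unchanged for control participants, since the physician may prescribe otherwise.

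**Conclusion.** The point holds in this form: data collection ends because of the outcome being counted, which truncates one primary and one secondary outcome and possibly the monthly review, and no planned analysis deals with it. The usual effect is to shrink an absolute excess in the arm with more persistent occlusion. Its size rests wholly on assumed visit frequency and persistence: 16% to 71% of the mean difference in step 4, with the t statistic falling at most from 1.86 to 1.60 and the rate ratio from 1.69 to 1.44. The direction depends on which arm has the more persistent ports. The sample size, the 10% margin, the first-occlusion outcomes and the formal looks are unaffected if terminated participants are analysed. It should be corrected, but it does not threaten the trial's central comparison.

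**What to change.** 1. Leave the clinical stopping rule as it is and separate it from data collection. For terminated participants, keep recording occlusions and alteplase use on the existing Record of Flushes to month 6, and analyse everyone by randomised arm.
2. Add a secondary maintenance-failure outcome: the proportion per arm who met the three-consecutive-visit rule or had the port removed for unresolved occlusion.
3. In the monthly review and the final analysis, express alteplase use per port access, beside that proportion, and name the review's data source. The denominator alone is not a cure, since the rate ratio in step 4 still falls.
4. Report counts up to the stop as well as counts to month 6, and say which question each answers.
5. Reconcile the two triggers: alteplase required, which includes sluggish withdrawal, under Data collection tool, and port found occluded under Experimental Aspect of the Study. The latter section also ends participation when a listed risk occurs and lists partial and complete occlusion among the risks. Read literally, that conflicts with a three-visit rule and must be reconciled too.

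**Cost.** Small: an existing form, at the same centres, for few people. In the worked case a persistent port meets the rule with probability 0.776, so about 198 × 0.05 × 0.776 = 8 control and 198 × 0.10 × 0.776 = 15 saline participants. The downside is that saline counts after the stop reflect mixed flushing, which is why item 4 is needed.

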Currently at TriHealth, Inc. all implanted port catheters are flushed according to the TriHealth Nursing Policy and Procedure Intravenous Site Guidelines (See Appendix A). An implanted port catheter is flushed with normal saline after IV medication, blood, or blood draws. Heparinized saline in the amount of 5 mL (concentration 100 units/mL) is used as a final flush when no IV fluids are running and before de-accessing. This is intended to maintain patency of the catheter until the next use. The same process is used at University of Cincinnati Medical Center Barrett Infusion Center, a new site added to the study in January 2018.

TriHealth wide, there is no accurate data describing either the number of port catheters that are in use or the specifics of the complication rate. This data also is lacking UCMC wide. During the period of time between May 2, 2011 and April 30, 2012, the Out-Patient Cancer Care (OPCC) at TriHealth, utilized 134 doses of alteplase (Cath-Flo) to resolve occlusions. There is no easily accessible data describing whether these were partial (flushable but without a blood return) or complete (unable to flush) occlusions. There is no easily accessible information summarizing the type of central line that had to be de-clotted; however, the majority (>95%) of central lines

utilized by cancer patients in the OPCC are single lumen implanted port catheters. During this time period, there were two patients receiving care in the OPCC whose catheters were not flushed with a heparinized saline solution. One patient has documented HIT, and the other has a reported heparin allergy. Both patients have been able to maintain patent catheters with saline only flushes. Hospital wide, information related to the diagnosis of HIT, as it relates to type of Heparin exposure (e.g., subcutaneous or IV Heparin or the use of heparinized saline) is not available. There are no data available that demonstrates that patients with implanted port catheters who have developed a partial or complete occlusion developed bacteremia or central line infection due to the presence of fibrin on their catheter. Development of a fibrin sheath on the catheter is common after placement of an implanted port catheter (Gallieni, Pittiruti, & Biffi, 2008). The fibrin sheath may then become seeded with microorganisms which may disseminate into the blood stream. Both catheter-related thrombus and bacteremia are potentially life-threatening conditions.

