Heparin induced thrombocytopenia (HIT) is an immune reaction to heparin. Through a series of steps, antibodies are produced in response to an immune complex, which in turn activates platelets. As activated platelets are destroyed, thrombocytopenia (low platelet count) occurs. This ultimately leads to a thrombotic state. Patients experiencing HIT can develop deep venous thrombosis, pulmonary emboli, stroke, or myocardial infarction. Patients developing HIT thrombotic syndrome may require limb amputation and are at increased risk for death. The actual incidence of HIT is 1-5% of patients exposed to heparin (Cooney, 2006). Many clinicians think that HIT is under-recognized and under diagnosed. The first response to the diagnosis of HIT is the discontinuation of all forms of heparin, including heparin flushes. The use of heparin should be avoided or minimized whenever possible. If saline only flushes were found to be as effective as heparinized saline flushes, it would significantly decrease the patient's exposure to heparin, and therefore the potential to develop HIT.

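### Ending the assigned flush also ends all data collection, so complications after HIT, repeated occlusion and other terminations go unrecorded, for reasons that differ by arm

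*Combined protocol and SAP*

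**What the plan says.** **Termination rules.** Experimental Aspect of the Study sets participation at 6 months or until one of the listed risks occurs. It then lists events that end both participation and recording:

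- HIT or heparin allergy: "Study participants who develop HIT (heparin induced thrombocytopenia) or other heparin allergy will be terminated and excluded from further data collection".
- Ports found occluded on three consecutive visits: these participants "will be excluded from further data collection, i.e., their participation in the study will be terminated".
- Port removal after failed alteplase: "Study participants whose occlusion cannot be resolved with alteplase and require removal of the port will also be terminated and excluded from further data collection".
- Port infection needing removal, and thrombosis or embolism needing therapeutic anticoagulation, under the same rule.
- A heparin flush given to a saline participant during other clinical care: withdrawal from the study.

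The Data collection tool section has a matching rule for alteplase on three consecutive visits: "the patient's participation in the study will be terminated and they will be excluded from further data collection". That participant then goes back to site-policy or physician-directed flushing.

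**Outcomes.** The complications among the secondary outcomes include "Central Line-Associated Blood Stream Infection (CLABSI) a laboratory-confirmed" line-associated infection, and HIT defined by a positive antibody test. Thrombotic events after HIT are not a listed outcome. Research question 2 asks whether the type and rate of complications differ between arms, and the stated purpose is to find the safest and most effective flush.

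**Background.** On HIT: "Patients experiencing HIT can develop deep venous thrombosis, pulmonary emboli, stroke, or myocardial infarction"; amputation and death are also named. On the catheter: "The fibrin sheath may then become seeded with microorganisms which may disseminate into the blood stream". The same background section says that no data show bacteremia or line infection developing in patients with occluded ports.

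**The concern.** Stopping an assigned treatment and stopping observation are separate decisions, and the protocol makes them one. For HIT, the record closes at diagnosis, before the harms that make HIT a reason to give up heparin could be seen. For repeated occlusion, the port may remain in use at the same center, but a later CLABSI would not be counted.

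The truncation depends on what happened to the participant, and the reasons fall unevenly. HIT will arise mainly in the heparin arm. Withdrawal for a heparin flush can occur only in the saline arm. Termination for occlusion may be more frequent on saline if saline is worse. Complication rates by arm would then rest on follow-up of different length, cut for different reasons. At stake are research question 2 and the safety half of the study's purpose. The counting of first occlusions is a separate matter.

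**Working it through.** **1. Headcount.** With 20% occlusion in both arms, margin 0.10, one-sided 0.05 and 80% power: n = (1.645 + 0.842)² × 2 × 0.20 × 0.80 / 0.10² = 197.8, so 198 per group, as stated. For consents, 396 / 0.697 = 568.1, so 569 against the stated 575, which is close. I use 575; equal allocation (assumed) gives 575 / 2 = 287.5, about 288 per arm.

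**2. Non-completion.** 575 × 0.303 = 174, or 575 − 396 = 179. So about 174-179 consented participants would not reach 6 months for any reason. The documents do not split this by reason or by arm.

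**3. HIT.** The background gives 1-5% of patients exposed to heparin. 287.5 × 0.01 = 2.9 and 287.5 × 0.05 = 14.4, so about 3-14 controls. This assumes that a general heparin-exposure figure applies to flushes. The protocol says that local HIT data by type of exposure are unavailable.

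**4. Where follow-up is lost, reason by reason.**

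| Reason | Arm mainly affected | What goes unrecorded |
|---|---|---|
| HIT or heparin allergy | Heparin | Later thrombosis, stroke, MI, death; later CLABSI |
| Three consecutive occluded or alteplase visits | Possibly saline | CLABSI while the port stays in place |
| Unresolved occlusion or infection, port removed | Unknown | Little later CLABSI unless a port is re-inserted |
| Therapeutic anticoagulation | Unknown | Everything after the event |
| Heparin flush in other care | Saline only | Everything after the flush |

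**5. Can the CLABSI bias be signed?** The documents give no CLABSI rate and no rate of repeated or unresolved occlusion, so every input here is assumed: 3% six-month risk in ports that are not terminated; a fraction f terminated for occlusion at month 3 (10% saline, 5% heparin); infection hazard multiplied by R afterwards; a share r of terminated ports removed and carrying no later risk.

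h = −ln(0.97)/6 = 0.00508 per month, and 1 − exp(−3h) = 1.511%.

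Recorded risk = (1 − f) × 3% + f × 1.511%. Saline: 0.90 × 3 + 0.10 × 1.511 = 2.851%. Heparin: 0.95 × 3 + 0.05 × 1.511 = 2.926%. Recorded difference (saline minus heparin): −0.07 points.

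Full risk = (1 − f) × 3% + f × [(1 − r)(1 − exp(−(3h + 3hR))) + r × 1.511%]. Full difference:

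- R = 1, r = 0: 0.00 points
- R = 3, r = 0: +0.15 points
- R = 3, r = 1/2: +0.04 points
- R = 3, r = 2/3: about 0.00 points

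If HIT terminations at month 3 are added to the heparin arm (f = 0.06 or 0.10), the recorded difference moves from −0.07 to −0.06 (1% HIT) or 0.00 (5% HIT). The standard error of the difference at 288 per arm is √(2 × 0.03 × 0.97 / 288) = 1.4 points. The answer therefore turns on unknown inputs, and every value is far below the sampling error.

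**The case against.** Much of the case on the other side concerns CLABSI, and most of that stands. A reader might infer that the participants cut off are those most at risk of infection, and that the missing events would turn a true excess on saline into an apparent advantage. The documents do not support either inference. The seeding mechanism is stated only as a possibility, the fibrin sheath is described as common after port placement generally, and the protocol says that it has no data linking occlusion to bacteremia. Removing a port also removes most of its later risk. A reversal of sign appears only if terminated ports are assumed to stay in and to carry a raised hazard; it fades with port removal, and HIT terminations in the heparin arm pull the other way.

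Two further objections stand in part. First, HIT is reported only as an antibody result because of the outcome definition, and the termination rule alone did not cause that. This is why later thrombotic events have to be added to what is recorded. Second, known heparin antibody carriers are excluded at entry and the 1-5% incidence is general, so 3-14 could overstate the HIT count.

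What the objections leave untouched is the text. Recording stops at the named events, and the protocol itself says that serious harm can follow one of them. HIT diagnoses, and any CLABSI up to termination, are still captured; a single resolved occlusion does not end follow-up.

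**Conclusion.** The point holds as a gap in safety follow-up that is informative and unequal by arm. It is firmest for HIT, where the protocol states the later harms outright: about 3-14 of about 288 consented controls, if the quoted incidence applies to flush exposure and allocation is equal. For CLABSI, follow-up is lost, chiefly where the port stays in place after three consecutive occluded visits. The direction and size of any resulting bias cannot be determined from the documents, and on the assumed inputs above it is small. The change is worth making because research question 2 is a comparison of complications and the remedy is cheap. One part of the protocol, after the heading on estimated time to complete the study, was not available to me. The conclusion assumes that it adds no safety follow-up.

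**What to change.** In Experimental Aspect of the Study and Data collection tool, separate stopping the assigned flush from stopping observation.

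- **Who.** Every participant terminated or withdrawn for any reason, including therapeutic anticoagulation and an off-protocol heparin flush, unless consent is withdrawn. Covering only some reasons would leave follow-up unequal by arm.
- **What.** To 6 months after enrolment, from the site chart: CLABSI while a port is in place, thrombotic or embolic events, port removal and death, with the date the assigned flush stopped.
- **Analysis.** Compare complications by randomised arm over all randomised participants. Show events after termination separately, since they occur off the assigned flush. Report HIT together with later thrombotic events.

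**Cost.** A protocol amendment, one chart review per terminated participant (at most about 174-179, if all non-completers are included), and a check that the consent form and HIPAA authorization cover it. No extra visits, tests or patients are needed. Eligibility already requires expected care at these centers for 6 months, and the enrollment log links study codes to medical records. That log is to be destroyed after data cleaning, so the review must come first. Records will be incomplete for participants who have moved their care. Clinical care after termination stays as written.
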